Influence of Custom Orthosis Post Carpometacarpal (CMC) Arthroplasty

NCT050307510

Document date: document created for submission to UToledo IRB. Approval date of IRB 2/21/22.

THE ELEMENTS OF A RESEARCH PROTOCOL

Influence of custom orthosis post CMC arthroplasty

1. Background, Review of the Literature, Significance

Carpometacarpal (CMC) osteoarthritis (OA) can cause severe pain and loss of hand function, thumb motion and thumb strength (Fontana et al., 2007). CMC arthroplasty, surgery on the thumb joint, is conducted when conservative treatments for CMC OA fail (Grenier et al. 2016). In 2011, 6,960 CMC arthroplasties were conducted in the United States (Werner et al., 2015). Splints or orthoses are typically used after surgery to immobilize the joint as the wound heals. Previous studies have reported mixed results in the comparison of outcomes related to use of custom orthoses and prefabricated splints (Baradaran et al., 2018; Sillem et al., 2011; Marotta et al., 2020; Bani et al., 2013). This study aims to compare post-surgical outcomes, including wound dehiscence, pain, function, and satisfaction with device and care from individuals who receive either a custom orthosis or prefabricated splint after CMC arthroplasty. This study will allow for increased understanding about the pros and cons of prefabricated splints versus custom orthosis which can inform clinical decisions in order to decrease wound dehiscence, the pain associated with wound dehiscence, and enhance function post-surgery for individuals who have CMC arthroplasty.

2. Objectives/Specific Aims

- To determine the difference in the incidence of wound dehiscence after a CMC arthroplasty when using a custom orthosis as compared to a prefabricated splint.
- To determine the difference in subject reported pain levels after a CMC arthroplasty between those who received a custom orthosis as compared to those who received a prefabricated splint.
- To determine the difference in function as measured by the QuickDASH, active range of motion measurements of the thumb, and subtests within the applied dexterity section of the Arthritis Hand Function Test (AHFT) between those wearing a custom orthosis as compared to those wearing a prefabricated splint.
- To determine the difference in subject satisfaction with device and services at the first and second post-operative appointment.

3. Methods

a) **Study Design**

- Experimental, two groups with random assignment

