b) **Method of treatment assignment**

Subjects will be randomly assigned using at the initial follow-up appointment following CMC arthroplasty. The surgeon may exclude the subject, following assessment, if the subject cannot be randomly assigned to an intervention group. Open-label blinding will be used since every member of the team will be able to perceive whether the subject has

received a custom orthosis or prefabricated splint. Random assignment to the two groups will be completed in SPSS.

c) Inclusion/exclusion criteria

Inclusion criteria for subjects include status post CMC arthroplasty (within 4-5 weeks), 18 or older, able to read and understand English, capable of independently consenting to health care procedures.

Subjects will be excluded from the study if the surgeon identifies risk factors that would preclude random assignment to the control or experimental group. Subjects will also be excluded if they request a prefabricated or custom orthosis.

d) Justification of the number of subjects

Anticipated number of subjects that will be requested for enrollment is 125 subjects. A sample size of at least 96 is required for a power of 60 with $\alpha = .05$.

e) Study setting

University of Toledo Medical Center (UTMC) outpatient.

f) Primary and secondary outcome measures

Primary Outcomes include:

Function - as measured by the QuickDASH

Wound dehiscence – as measured by the Sandy Grading System

Pain - as measured by the Visual Analog Pain Scale

Thumb CMC Active Range of Motion (AROM) measurements

Subtests within the applied dexterity section of the Arthritis Hand Function Test

Satisfaction with device and services – as measured by the OPUS.

Secondary variables of interest include:

Demographic data such as age, gender, race, handedness, pre-existing conditions current medications and supplements, smoking history, and alcohol consumption.

h) Procedures, interventions, schedule

FIRST POST-OP APPOINTMENT

Standard of care: At the initial post-op appointment with the surgeon, the client will check in and register for the appointment. A member of the surgical team will assess the client and document the Sandy Score.

Research specific: As a member of the surgical team assesses the client he/she will determine if the client meets the inclusion criteria. If the client does meet the inclusion criteria, the study will be briefly explained using the recruitment flyer. The client will then be asked if he/she is interested in participating.

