If the client is interested in participating, a member of research team will meet with the client to review the consent form and answer any questions. Once any questions have been answered, if the subject agrees to participate, he/she will sign the informed consent form. The subjects will be informed both verbally and in writing that they can take consent away at any

time during the research study. A copy of the informed consent form will be given to the subject. The client will be randomly assigned to intervention A or intervention B.

Standard of Care: The subject will receive either a prefabricated splint (Intervention A) or custom orthosis (Intervention B).

Research specific: The subject will then be asked to complete the demographic questionnaire, QuickDASH, and the Pain VAS. Thumb CMC active range of motion measurements will then be collected (radial and palmar abduction). Participants will also complete subtests within the applied dexterity section of the Arthritis Hand Function Test and OPUS survey.

Subjects who are assigned to Intervention A (the prefabricated splint group) will be provided a splint by a member of the surgical team. Subjects who are assigned to Intervention B (the custom orthosis group) will be evaluated by an occupational therapist and a custom orthosis will be fabricated.

SECOND POST-OP APPOINTMENT

Standard of Care: Approximately 4-5 weeks later, subjects will attend a second post-op appointment and be assessed by a member of the surgical team. The Sandy score will be documented.

Research specific: At this time, a member of the research team will ask the subject to complete the, QuickDASH, and the Pain VAS. Thumb CMC active range of motion measurements will then be collected (radial and palmar abduction). Participants will also complete subtests within the applied dexterity section of the Arthritis Hand Function Test and OPUS survey.

i) Planned data analysis

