Means and standard deviations will be calculated for the demographic information such as age and alcohol consumption per week. In-group and between-group percentages will also be calculated for demographic information, such as gender, pre-existing diabetes, and smoking history. The means and standard deviations of scores received on the QuickDASH, Sandy Grading System, Pain VAS, and AROM will be calculated. In-group and between-group descriptive statistics will be calculated for scores on the OPUS and Applied Dexterity section of the Arthritis Hand Function test. Independent student t-tests will be conducted to compare the means between Interventions A and B. Dependent student t-tests will be conducted to compare the initial post-op assessment mean data to the second post-op assessment mean data within groups. P-values will be considered significant if they are less than or equal to 0.05.

4. Reference List

Baca, M. E., Rozental, T. D., McFarlane, K., Hall, M. J., Ostergaard, P. J., & Harper, C. M. (2020). Trapeziometacarpal joint arthritis: is duration of symptoms a predictor of

surgical outcomes? *The Journal of Hand Surgery*, 45(12), 1184.e1-1184.e7. <https://doi.org/10.1016/j.jhsa.2020.05.026>

Bani, M. A., Arazpour, M., Kashani, R. V., Mousavi, M. E., & Hutchins, S. W. (2013). Comparison of custom-made and prefabricated neoprene splinting in patients with the first carpometacarpal joint osteoarthritis. *Disability & Rehabilitation: Assistive Technology*, 8(3), 232–237. <https://doi.org/10.3109/17483107.2012.699992>

Bani, M. A., Arazpour, M., Kashani, R. V., Mousavi, M. E., Maleki, M., & Hutchins, S. W. (2013). The effect of custom-made splints in patients with the first carpometacarpal joint osteoarthritis. *Prosthetics and Orthotics International*, 37(2), 139–144. <https://doi.org/10.1177/0309364612454047>

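### Whether the operated hand is the dominant one is neither named as a variable nor used in the between-arm tests, at a modest cost in precision for QuickDASH and the AHFT subtests

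*Combined protocol and SAP*

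**What the plan says.** Section 2 states the function aim: "To determine the difference in function as measured by the QuickDASH, active range of motion measurements of the thumb, and subtests within the applied dexterity" part of the AHFT. Section 3.f lists all three measures as primary outcomes.

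The secondary variables in 3.f are "Demographic data such as age, gender, race, handedness, pre-existing conditions current medications and supplements, smoking history, and alcohol consumption". Handedness is there. The operated side is not, and it appears nowhere else in the document. The list is given as examples, and the demographic questionnaire mentioned in 3.h is not reproduced.

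Section 3.i uses the demographic variables for description only, for example "In-group and between-group percentages will also be calculated for demographic information, such as gender, pre-existing diabetes, and smoking history". For the comparison of arms it says "Independent student t-tests will be conducted to compare the means between Interventions A and B". It names no covariate or stratum. The first-visit scores are tested only within arms: "Dependent student t-tests will be conducted to compare the initial post-op assessment mean data to the second post-op assessment mean data within groups".

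Section 3.d gives a minimum of 96 subjects for a power of 60 (read here as 60%) at a 0.05 significance level, and expects to ask 125 people to enrol.

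**The concern.** QuickDASH asks about everyday use of the arm and hand, and the applied dexterity subtests are hand tasks. A few weeks after thumb surgery, both are likely to depend on whether the operated hand is the dominant one. Handedness informs this only when paired with the operated side, and the plan names just one of the two.

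Dominance of the operated hand is settled at surgery, before assignment, and the device cannot change it. That makes it a legitimate covariate. An unadjusted t-test leaves its contribution in the residual variance. If the side is not recorded, a reader also cannot see from a baseline table whether the arms happened to differ on it. In a trial planned at 60% power, precision available without extra subjects deserves a look.

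**Working it through.** **The plan's own figure.** The 96 in 3.d cannot be reproduced: no endpoint, effect size, SD, event rate, sidedness or allocation ratio is given. It can be back-solved. Assuming 1:1 allocation (48 per arm) and a two-sided 0.05 test of two means, the standardised effect is

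d = (1.960 + 0.2533) × √(2/48) = 0.452 SD (0.456 with the t distribution).

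A one-sided test would imply 0.39 SD. A comparison of assumed proportions of 5% and 20% also returns 96, so the figure does not identify one endpoint. I use d = 0.452 only as a 60% power reference point.

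**Assumptions not in the documents.**
- q, the share operated on the dominant side: 0.5, varied to 0.7.
- g, the difference in mean score between dominant-side and other-side surgery, in SDs within each of those two groups: 0.3, 0.5 and 0.8.

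**Dominance term alone.** With V = 1 + q(1−q)g², the share of variance removed is R² = 1 − 1/V. Power is Φ(2.2133/√(1−R²) − 1.960), and the equivalent unadjusted sample size is 96 × V.

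| g | V | R² | Power | Equivalent N |
|---|---|---|---|---|
| 0.3 | 1.0225 | 2.2% | 61.0% | 98 |
| 0.5 | 1.0625 | 5.9% | 62.6% | 102 |
| 0.8 | 1.1600 | 13.8% | 66.4% | 111 |

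The value q = 0.5 gives the largest gain. At q = 0.4 or 0.6 the powers are 60.9%, 62.5% and 66.2%. At q = 0.7 they are 60.8%, 62.2% and 65.4%. If g = 0 for an outcome, nothing is lost.

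**Chance imbalance.** The 95% limit for the difference between arms in the share with dominant-side surgery is 1.96 × √(2 × 0.25/48) = 0.20. The resulting shift in the arm difference is 0.20 × g/√V, which is 0.06, 0.10 or 0.15 SD. The t-test's standard error already allows for this. It is the same loss seen from another side, not a second one.

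**Dominance on top of the visit-1 score.** Assume the same shift g at both visits and a correlation r between visits within each dominance group. The overall correlation is ρ = (r + q(1−q)g²)/V. The residual variance share is 1 − ρ² with the visit-1 score alone and (1 − r²)/V with both terms. For g = 0.5 and q = 0.5:

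| r | 1 − ρ² | (1 − r²)/V | Power, visit-1 score alone | Power, both | Added by dominance |
|---|---|---|---|---|---|
| 0.3 | 0.884 | 0.856 | 65.3% | 66.7% | 1.4 points |
| 0.5 | 0.720 | 0.706 | 74.2% | 75.0% | 0.8 points |
| 0.7 | 0.485 | 0.480 | 88.8% | 89.2% | 0.3 points |

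Differences are taken before rounding. The visit-1 score is the stronger covariate and carries much of the dominance effect if that effect is present at both visits.

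**The case against.** The strongest reply is that little is missing. The 3.f list is open-ended and the questionnaire is not shown. The side is known at the point of care: at the first visit "A member of the surgical team will assess the client and document the Sandy Score", a device is fitted to the thumb, and "Thumb CMC active range of motion measurements will then be collected (radial and palmar abduction"). A reader might infer that the trial will not know which thumb was operated on and could never account for it. The documents do not support that; they show only that the plan does not name the item. This part of the reply stands.

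It also stands that recording the side would by itself change no result, because 3.i adjusts for nothing. The field matters only together with a model term.

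The size of the dominance effect is assumed, since the documents give none for any outcome. At 0.3 to 0.5 SD the gain is worth 2 to 6 subjects, against 125 to be approached and 96 required. A reader might also infer a material loss on all three function outcomes. AROM is a joint-angle measure, and an effect of dominance is least evident there.

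Finally, the visit-1 score is a better covariate and is already collected. That is right, and it belongs in the model. It does not make dominance redundant, because 3.h lists the visit-1 measures after open-label assignment and after receipt of the device. As scheduled, those scores could be touched by knowledge or use of the device; dominance cannot.

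**Conclusion.** The point holds as a small matter of efficiency and reporting. The plan names handedness but not the operated side, and its between-arm t-tests leave dominance of the operated hand in the error term for QuickDASH and the AHFT subtests. A reader might take this for bias or an invalid test. It is neither: assignment is random, so the unadjusted comparison stays valid and the expected imbalance is zero.

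Dominance adjustment alone is worth about 1, 3 or 6 power points from a 60% base at assumed effects of 0.3, 0.5 or 0.8 SD. At 0.5 SD it is worth 0.3 to 1.4 points once the visit-1 score is in the model. These figures rest on 48 per arm, a two-sided test, half the subjects operated on the dominant side and, for the last range, the same dominance effect at both visits with correlations of 0.3 to 0.7. Priority is low, but the change is nearly free.

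**What to change.** - **Section 3.f:** add operated side, taken from the surgical record, and derive *operated hand is dominant: yes/no*.
- **Section 3.i:** for QuickDASH and each AHFT subtest, replace the between-arm t-test with a linear model of the visit-2 score on arm, the yes/no dominance term and the visit-1 score. Report the adjusted arm difference with its 95% CI. The same model is optional for AROM.
- **Section 3.h:** if the visit-1 score is to serve as a true baseline, schedule its measurement before the device is assigned or fitted.

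The cost is one data field, one or two degrees of freedom per model and, for the last item, a changed order of steps within the first visit. No extra visit or subject is needed.

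### Section 3.h takes first-visit QuickDASH, pain VAS, AROM and AHFT after open-label assignment, so these four primary outcomes have no assured pre-assignment value

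*Combined protocol and SAP*

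**What the plan says.** Section 3.h (first post-op appointment) sets out the visit in order. The Sandy score is documented, eligibility is judged and consent is signed. Next, "The client will be randomly assigned to intervention A or intervention B". Next, "The subject will receive either a prefabricated splint (Intervention A) or custom orthosis (Intervention B". Only after that comes "The subject will then be asked to complete the demographic questionnaire, QuickDASH, and the Pain VAS", then AROM, and in the same block the AHFT subtests and OPUS.

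A later paragraph of 3.h describes device provision again. The prefabricated group "will be provided a splint by a member of the surgical team"; the custom group "will be evaluated by an occupational therapist and a custom orthosis will be fabricated".

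The measures are repeated once: "Approximately 4-5 weeks later, subjects will attend a second post-op appointment".

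Section 3.b calls the trial open-label because "every member of the team will be able to perceive whether the subject has" received one device or the other, and says only that SPSS produces the assignment. Section 3.c adds: "Subjects will also be excluded if they request a prefabricated or custom orthosis". Section 3.f lists QuickDASH, pain VAS, AROM and the AHFT subtests among the primary outcomes. Section 3.i plans paired t-tests of first against second visit within each group, and independent t-tests between groups with no visit named and no baseline adjustment.

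**The concern.** A baseline is safe to compare with or adjust for only if the treatment cannot have influenced it. QuickDASH and VAS are self-reported, and AROM and AHFT depend on effort. If a participant or assessor already knows the allocation, or the device is already on, any resulting shift is part of the first-visit value.

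The shift would then enter every analysis that uses that value: the planned paired tests, a between-arm comparison at the first visit, a change score, an ANCOVA, and any check that the arms were comparable at the start. The pain and function aims in section 2 are comparisons between devices. For those aims, the main loss is that the trial has no assured clean value to adjust for.

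**Working it through.** **1. Order of steps.** Both descriptions of device provision in 3.h come after assignment, so the measures follow assignment on either reading. What stays open is whether the device is merely assigned, known, or already worn when they are taken. No section withholds the allocation, and no preoperative or other earlier measurement of these four outcomes is planned. The Sandy score is different: it is documented before consent and assignment.

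**2. Inputs for an illustration.** From section 3.d: at least 96 participants, power 60, alpha 0.05. The 96 cannot be reproduced, because no effect size, SD, sidedness or allocation ratio is given. Assumed here: 96 is the total, split 48 per arm; the test is two-sided; 60 means 60%; SD is 1 at both visits; the between-visit correlation r is 0.5 (range 0.3 to 0.7); the first-visit shift is 0.2 SD in one arm. Power is from the noncentral t distribution.

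Back-solving for an independent t-test: noncentrality d × √(48/2) = d × √24 on 94 df gives 60% power at d = 0.456.

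**3. Paired test within one arm.** Noncentrality = δ × √48 / √(2(1 − r)), 47 df.

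- No true change, shift at visit 1 only: δ = 0.2, r = 0.5 gives 0.2 × 6.928 / 1 = 1.386. The test rejects 27% of the time instead of 5% (21% at r = 0.3, 42% at r = 0.7).
- Equal shift at both visits: δ = 0, rejection 5%.
- True change 0.3 SD, r = 0.5: power 53%. With the shift, the net change is 0.1 or 0.5 SD and power is 10% or 92%.
- True change 0.8 SD, r = 0.5: power over 99.9%. With a net change of 0.6 SD it is 98% (at r = 0.3, 99.6% and 93%).

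**4. Unadjusted second-visit t-test.** The first-visit value is not used, so a first-visit shift leaves rejection at 5%. A 0.2 SD reporting shift at the second visit gives noncentrality 0.2 × √24 = 0.98 and 16% rejection, whatever the order at the first visit.

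**5. ANCOVA on the first-visit value.** The estimate is the second-visit difference minus r times the first-visit difference. Noncentrality = estimate × √24 / √(1 − r²), 93 df. A 0.2 SD first-visit shift therefore biases the estimate by 0.2r, in either direction.

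| | r = 0.3 | r = 0.5 | r = 0.7 |
|---|---|---|---|
| Power, unshifted first-visit value, true d = 0.456 | 64% | 72% | 87% |
| Estimate if the shift is in the better arm, towards benefit | 0.396 | 0.356 | 0.316 |
| Power in that case | 52% | 51% | 57% |
| Estimate if the shift is reversed | 0.516 | 0.556 | 0.596 |
| Power in that case | 75% | 88% | 98% |
| Rejection with no true difference | 6% | 9% | 16% |

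The higher power in the reversed case is not a benefit; the estimate is too large.

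**The case against.** The strongest reply is that the aims are between-device comparisons, section 3.i plans unadjusted t-tests for them, and a second-visit t-test does not depend on the first-visit order. That stands. A reader might infer that the randomised comparison is invalid; the documents do not support this. It is limited by 3.i naming no visit, so a first-visit or change-score comparison is not excluded.

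Second, the plan never calls the first visit a baseline. The function aim speaks of people wearing each device, and OPUS at that visit asks about the device, so a device-on measurement may have been intended. That is possible, but 3.i still uses these values as the starting point of significance tests.

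Third, a reader might say that 3.h contradicts itself on device provision. That is too strong. The later paragraph carries no time word and may only say who supplies which device. It is an ambiguity to be reconciled.

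Fourth, a reader might infer that participants are told their allocation before completing the measures, or that concealment fails at enrolment. Nothing states the former; the text only fails to prevent it. As for the latter, consent and eligibility precede assignment in 3.h, and this point concerns only the withholding of the result until the measures are done. Excluding people who request a device may reduce expectation effects but does not remove them.

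Fifth, the paired-test figure of 27% assumes no true change over 4-5 weeks of postoperative recovery. With large recovery the effect on power is small, as the 0.8 SD case shows.

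**Conclusion.** The point holds in a limited form. As written, four primary outcomes have no assured pre-assignment value, and 3.h leaves the timing of the device relative to the measures unclear. The exposed analyses are the planned within-group paired tests and any first-visit, change-score or baseline-adjusted between-arm comparison.

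The documents give neither the size nor the direction of any shift. Under the assumptions above, an ANCOVA would be biased by about 0.2r SD either way (0.06, 0.10 and 0.14 SD at r = 0.3, 0.5 and 0.7).

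A reader might credit the reorder with the rise from 60% to 72% power. That would be wrong: the gain comes from the adjustment, and an unshifted post-assignment value would give the same. What the reorder does is protect the adjustment from bias. This merits a short amendment; it does not undermine the trial as a whole.

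**What to change.** In 3.h, state that demographics, QuickDASH, VAS, AROM and AHFT are completed after consent and before the assignment is generated or revealed, with OPUS left until after the device is received. Reconcile the two device-provision passages; when the device is provided is for the study team to settle.

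In 3.i, state that the arms are compared on second-visit values of these four outcomes by ANCOVA adjusted for the pre-assignment value. State also that the within-group paired tests describe change over time and are not evidence of a device effect.

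The cost is a short amendment and holding back the SPSS assignment within the same visit, with no added visits or measurements. There are three downsides:

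- Any intended device-on measurement at the first visit is given up.
- Reporting bias that would have been equal at both visits no longer cancels in the paired tests (5% becomes 27% in the illustration), which is a further reason to keep them descriptive.
- Open-label reporting bias at the second visit is not cured.

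### Aim 1 asks for the incidence of wound dehiscence, but the plan records one wound grade after assignment, states no look-back, and compares mean grades only

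*Combined protocol and SAP*

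**What the plan says.** Section 2 lists this aim first: "To determine the difference in the incidence of wound dehiscence after a CMC arthroplasty", custom orthosis against prefabricated splint. Section 3(f) names dehiscence among the primary outcomes, "as measured by the Sandy Grading System", without saying which grade counts as an event or over what period.

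Section 3(h) gives the order of events. At the first post-op appointment, "A member of the surgical team will assess the client and document the Sandy Score". Eligibility, consent and allocation come after that: "The client will be randomly assigned to intervention A or intervention B". The next contact described is the second appointment: "Approximately 4-5 weeks later, subjects will attend a second post-op appointment and be assessed by a member of the surgical team". There, "The Sandy score will be documented". No wound check, telephone call, diary, chart review or adverse-event form is described between the two visits.

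Section 3(i) handles the score together with the continuous measures: "The means and standard deviations of scores received on the QuickDASH, Sandy Grading System, Pain VAS, and AROM will be calculated". Independent t-tests then compare the arms, and paired t-tests compare the two visits within each arm. No count or proportion of patients with dehiscence is planned.

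**The concern.** Incidence means new events over a period at risk. The visit-1 score comes before the device, so it is a baseline. One reading at the end of the interval shows which wounds are open then, which is point prevalence. The two differ in two ways:

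- A wound that opened and healed between visits would probably be graded as intact at visit 2.
- A wound open at visit 1 and still open at visit 2 is mixed with wounds that opened under the assigned device.

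The analysis section does not close the gap. A difference in mean grade is not a difference in incidence, and the between-arm t-test uses no baseline score. At stake is whether the trial can report the quantity that its first aim promises, and with how much power.

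**Working it through.** **1. Count the readings.** Sandy scores before assignment: 1. Between assignment and visit 2: 0. At visit 2: 1. Event variables defined in section 3(i): 0.

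**2. The plan's own figure.** Section 3(d) gives a minimum of 96 subjects for a power of 60 (read as 60%) at α = 0.05. It names no outcome, effect size or event rate, so 96 cannot be derived forward. Solved backwards with 48 per arm (1:1 assumed), a two-sided comparison of means gives d = (1.960 + 0.253) × √(2/48) = 0.452. For proportions, 5% vs 20% also returns it:

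n per arm = [1.960 × √(2 × 0.125 × 0.875) + 0.253 × √(0.05 × 0.95 + 0.20 × 0.80)]² / 0.15² ≈ 47.3, rounded up to 48, or 96 in total.

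Other rate pairs give 96 as well, so this does not show what the sponsor assumed. It only makes 5% vs 20% a convenient illustration.

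**3. Effect of missed events.** If a share h of new events has healed and is graded as none in both arms, observed incidence = true incidence × (1 − h). The table gives exact power of a two-sided Fisher test at 48 per arm. All rates and values of h are assumptions.

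| h | 5% vs 20% observed as | Power | 10% vs 30% observed as | Power |
|---|---|---|---|---|
| 0 | 5% vs 20% | 0.481 | 10% vs 30% | 0.613 |
| 0.10 | 4.5% vs 18% | 0.415 | 9% vs 27% | 0.541 |
| 0.25 | 3.75% vs 15% | 0.313 | 7.5% vs 22.5% | 0.425 |
| 0.50 | 2.5% vs 10% | 0.145 | 5% vs 15% | 0.227 |

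The 0.481 is below 60% because the Fisher test is more conservative than the normal approximation in step 2. At 2% vs 8%, power is only 0.083 even with full capture.

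**4. Effect on the estimate.** With equal h in both arms, the risk difference shrinks by (1 − h) and the risk ratio is unchanged. With unequal h, the ratio moves too. Take true rates of 20% vs 10%, with 75% and 50% healed by visit 2. The observed rates are 20% × 0.25 = 5% and 10% × 0.50 = 5%, a ratio of 1.0 where the true ratio is 10/20 = 0.5.

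**5. Effect of wounds already open.** Suppose a share b in each arm is open at visit 1 and stays open. The visit-2 proportion is then b + (1 − b)p, where p is the true incidence. For 5% vs 20%:

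- b = 5%: 9.75% vs 24%, power 0.36 (0.48 when b = 0).
- b = 10%: 14.5% vs 28%, power 0.28.

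The risk difference is 15 × (1 − b) points, that is 14.25 and 13.5 points. The contrast is diluted in the same way whichever device a patient receives.

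**The case against.** A reader might infer three stronger things that the documents do not support.

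- **That a healed dehiscence is certain to be scored as none.** The plan states no look-back rule either way, and the definition of the grading system lies in a source outside the documents. An assessor could notice or be told of a healed episode. Grading the wound as it is that day is the plain reading, not a stated rule. What stands is that nothing tells the assessor to record such an episode.
- **That wounds already open count against one device.** Assignment is random and follows the visit-1 score, so such wounds are balanced in expectation. They dilute the contrast and cost power; they do not penalise an arm. The surgeon may also exclude patients with risk factors (section 3(c)), although the plan does not say whether an open wound is one. The score needed to separate old from new is already collected, so this part needs a definition and no new measurement.
- **That the comparison between devices is biased.** That requires healing, or its detection, to differ by device. The documents give no evidence of this, and step 4 shows only what would follow if it did.

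It is also fair to object that the power figures use a test the plan does not use and healed shares with no basis in the documents. With 10% missed the loss is modest (48% to 42%), and at low event rates missed healing is not what limits the trial. Finally, better capture alone would still feed a mean grade, so the missing event definition in section 3(i) is the more direct gap. All of this is accepted. It limits the size of the point but leaves the mismatch between Aim 1 and the planned data and analysis.

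**Conclusion.** The point holds in a limited form and is worth fixing. As written, the plan yields wound status at visit 2, summarised as a mean grade, and not the incidence that Aim 1 asks for. The schedule and section 3(i) establish this without any assumed rate.

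The consequences are less certain. Missed episodes and unseparated pre-existing wounds both lower power. Missed episodes distort the comparison only if healing differs by device. The amount cannot be known from the documents. Under 5% vs 20%, 48 per arm and a two-sided Fisher test, power runs from 48% with full capture to 15% with half the events missed. These figures show direction and scale under stated assumptions and are not estimates for this trial.

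**What to change.** 1. **Section 3(i), endpoint and test.** Define the Aim 1 event as dehiscence new since assignment, that is, absent on the visit-1 Sandy score, and state which grades count. Compare the proportion with an event between arms by Fisher exact test, with a confidence interval for the risk difference. Keep the mean or visit-2 grade as description. Report how many wounds in each arm were open at visit 1. This step uses data already planned and costs only text.
2. **Section 3(h), second appointment.** Add one item, worded and asked identically in both arms, recording any dehiscence since visit 1 and its worst grade. Support it with the surgical team's chart notes, which both arms have. The cost is one form line and a chart look-up at a visit already scheduled.
3. **Sensitivity.** Report the result with and without events known only from recall or chart. Section 3(b) makes the trial open-label, and under section 3(h) only the custom arm is evaluated by an occupational therapist. Capture could therefore differ by arm, and an identical question does not fully prevent that. Some recall error and possible differential capture are the price of step 2.
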